8.1.1 Aberrant Behavior Checklist-Community (ABC-C)

The Aberrant Behavior Checklist-Community (ABC-C) is a 58-item questionnaire completed by the LAR/caregiver that assesses a wide range of behaviors, including irritability, lethargy/social withdrawal, inappropriate speech, hyperactivity, stereotypic behavior, and social avoidance. Each item is rated on a scale of 0 to 3 (“not at all a problem” to “the problem is severe in degree”). The ABC-C will be scored 2 ways: according to the original method used to assess a population with a variety of disabilities ([Aman et al 1985](#)) and according to a method adapted for FXS that has a 6-factor structure ([Sansone et al 2012](#)).

The original method includes 5 subscales with the sub scores derivation:

SUBSCALES	Sum of Questions
Irritability	2, 4, 8, 10, 14, 19, 25, 29, 34, 36, 41, 47, 50, 52, 57
Lethargy/Social Withdrawal	3, 5, 12, 16, 20, 23, 26, 30, 32, 37, 40, 42, 43, 53, 55, 58
Stereotypic Behavior	6, 11, 17, 27, 35, 45, 49
Hyperactivity	1, 7, 13, 15, 18, 21, 24, 28, 31, 38, 39, 44, 48, 51, 54, 56
Inappropriate speech	9, 22, 33, 46

The method adapted for FXS subscales will be derived as follows:

SUBSCALES	Sum of Questions
Irritability	2, 4, 7, 8, 10, 14, 18, 19, 21, 24, 29, 34, 36, 41, 47, 50, 52, 57
Hyperactivity	1, 13, 15, 31, 38, 39, 44, 48, 54
Lethargy/Social Withdrawal	12, 20, 23, 25, 28, 32, 37, 40, 43, 51, 53, 55, 56, 58
Social Avoidance	5, 16, 30, 42
Stereotypic Behavior	6, 11, 17, 35, 45, 49
Inappropriate speech	9, 22, 33, 46

The mean change of ABC-C total and subscale scores according to the original method and according to the method adapted for FXS, at Week 2, Week 6, and Week 12 from baseline will be analyzed as described in [Section 8.1](#).

For ABC-C, the maximum amount of missing data that can be tolerated varies by subscale in original method. The following upper limits of missing items tolerated for each subscale are: (I) Irritability (15-item scale): 3 items; (II) Lethargy/Social Withdrawal (16-item scale): 3 items; (III) Stereotypic Behavior (7-item scale): 2 items; (IV) Hyperactivity/Noncompliance (16-item scale): 3 items; (V) Inappropriate Speech (4-item scale): 1 item. If more items than the stated upper limit have been left blank (unscored) by the rater, then the associated subscale score is not computed at all; instead, list the data as missing for those subscales.

When the amount of missing data is tolerated, subscale scores will be prorated as follows: (a) Take the total number of items on the subscale and divide this by the number of completed items. This will result in a number larger than 1.00. (b) Multiply that number by the total score for that subscale. (c) This becomes the new total score for this subscale for the given subject. For example, values of 13 items out of 15 Irritability questions are applicable with a sum of 23, then the prorated score of Irritability is $(15/13)*23=26.54$.

For subscales in FXS method, if the traditional subscales can be derived then the corresponding FXS subscale scores will be calculated. For FXS Social Avoidance subscale (4-item scale), if more than 1 item is missing then the subscale will be missing. Assuming values of 14 items out of 18 FXS-Irritability questions are applicable with a sum of 25, as the original Irritability is calculated, the FXS-Irritability score is prorated as $(18/14)*25=32.14$.

Subjects with total score of 16 or lower at the Baseline visit will be excluded from analysis of ABC-C, while sensitivity analysis with all subjects involved will be conducted.

The ABC-C total score will be calculated only when all associated subscales scores are derived and not missing.

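### FXS-adapted ABC-C subscales are accepted or refused by counting blanks in the traditional subscales, whose items differ, so FXS Lethargy can be prorated with 7 of 14 items missing

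*SAP*

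**What the plan says.** SAP 8.1.1 scores the ABC-C by the traditional method (five subscales, 58 items) and by an FXS-adapted method (six subscales), and prints the item list for each subscale. Protocol 6.3.1.1 says that only Inappropriate Speech is unchanged between the two; four factors are modified and one is new.

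The missing-item limits are set for the traditional subscales, for example "I) Irritability (15-item scale): 3 items", "II) Lethargy/Social Withdrawal (16-item scale): 3 items" and "III) Stereotypic Behavior (7-item scale): 2 items". Hyperactivity has a limit of 3 of 16 and Inappropriate Speech 1 of 4. Within the limit the score is prorated; beyond it the subscale is missing.

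For the FXS subscales the rule is that "if the traditional subscales can be derived then the corresponding FXS subscale scores will be calculated". One FXS subscale has a limit on its own items: "For FXS Social Avoidance subscale (4-item scale), if more than 1 item is missing then the subscale will be missing". A worked example prorates FXS Irritability from 14 of 18 items because the original Irritability subscale is available.

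A total score needs all of its subscales. SAP 11.2 only refers back to 8.1.1. SAP 3.2.2 and Protocol 7.2 list the FXS factor score among the secondary endpoints.

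**The concern.** A missing-item limit is meant to ensure that enough of a scale was answered for its prorated score to be trusted. Here the count is taken on a different set of items from the one being scored. Two errors become possible:

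- An FXS subscale can be prorated from too few of its own items, because imported items are never counted.
- An FXS subscale with every item answered can be refused, because the blanks lie in items that it does not use.

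The FXS Lethargy list, "12, 20, 23, 25, 28, 32, 37, 40, 43, 51, 53, 55, 56, 58", shows the problem: items 25, 28, 51 and 56 are not in traditional Lethargy. At stake is the validity and completeness of a secondary endpoint in arms of about 10 to 12 subjects (30 evaluable or 36 enrolled, divided by 3).

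**Working it through.** **The SAP's own figures.** Proration is (items on the subscale ÷ items answered) × observed sum. (15/13) × 23 = 26.54 and (18/14) × 25 = 32.14; both match the SAP. The item lists also match the stated sizes: 15 + 16 + 7 + 16 + 4 = 58 traditional, and 18 + 9 + 14 + 4 + 6 + 4 = 55 FXS (items 3, 26 and 27 are unused).

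**Most items that can be missing while the FXS score is still calculated.** Inputs are the item lists and limits in SAP 8.1.1. Under the same-named reading, the maximum is the traditional limit (all of it falling on shared items) plus the number of imported items.

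| FXS subscale | Items | Imported, not counted | Traditional limit | Maximum missing |
|---|---|---|---|---|
| Lethargy | 14 | 25, 28, 51, 56 | 3 of 16 (19%) | 3 + 4 = 7 of 14 (50%) |
| Irritability | 18 | 7, 18, 21, 24 | 3 of 15 (20%) | 3 + 4 = 7 of 18 (39%) |
| Hyperactivity | 9 | none | 3 of 16 (19%) | 3 of 9 (33%) |
| Stereotypic | 6 | none | 2 of 7 (29%) | 2 of 6 (33%) |
| Inappropriate Speech | 4 | none | 1 of 4 (25%) | 1 of 4 (25%) |

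A pattern that reaches the Lethargy maximum is 12, 20, 23, 25, 28, 51 and 56 blank. The traditional counts are then Lethargy 3, Irritability 1 and Hyperactivity 3, all within limits. The 50% therefore stands even if all five traditional subscales must be derivable. Under that wider reading Irritability falls to 3 + 3 = 6 of 18 (33%), because the imported items all belong to traditional Hyperactivity, with its limit of 3.

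At 7 of 14 the proration factor is 14/7 = 2.00. At the traditional Lethargy limit it is 16/13 = 1.23. SAP 8.2.1.4 refuses a CSHQ subscale at exactly this level, 50% missing.

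**Fewest own items missing when the condition fails.** This is max(0, limit + 1 − items counted but not scored).

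- Hyperactivity: counted but not scored are 7, 18, 21, 24, 28, 51, 56, so max(0, 3 + 1 − 7) = 0.
- Lethargy: 3, 5, 16, 26, 30, 42, so max(0, 3 + 1 − 6) = 0.
- Irritability: 25 only, so 3 + 1 − 1 = 3.
- Stereotypic: 27 only, so 2 + 1 − 1 = 2.
- Inappropriate Speech: none, so 1 + 1 − 0 = 2.

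A fully answered subscale can thus be blocked for Hyperactivity and Lethargy only, in each case by four blanks among the items listed.

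**Effect on the FXS total.**

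- *Lethargy route.* Of the six blocking items only 3 and 26 lie outside Social Avoidance (5, 16, 30, 42). Four blanks therefore include at least two Social Avoidance items, so that subscale is missing by its own rule and the total is lost in any case.
- *Hyperactivity route.* With 7, 18, 28 and 51 blank, traditional Hyperactivity has 4 missing and fails. FXS Hyperactivity has 9 of 9 answered, FXS Irritability lacks 2 of 18 and FXS Lethargy 2 of 14. Here the FXS total is lost only because of the rule.

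The SAP's worked example can meet the same problem. It does not say which four items are blank; if they are 7, 18, 21 and 24, FXS Irritability is prorated while FXS Hyperactivity is refused with all nine items answered.

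**The case against.** Four points on the other side deserve weight.

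- **The rule says *if*, not *only if*.** The SAP does not state that an FXS subscale is otherwise missing, whereas it does say so for Social Avoidance, and the FXS subscales are printed as plain sums of items. This stands in part: the loss of fully answered subscales is an inference. No other rule for calculating them is stated, so a programmer would have to guess.
- **The problem is narrower than it may look.** A reader might infer that any FXS subscale can be half empty, or that any complete one can be dropped. The item lists do not support that. The 50% belongs to Lethargy alone, and loss of a complete subscale to Hyperactivity and Lethargy. FXS Hyperactivity and Stereotypic items lie wholly inside their namesakes; there the limit is merely sized for a longer scale. A reader might also infer that the FXS total is needlessly lost by both routes, but only the Hyperactivity route does this.
- **The worked example is not extreme.** Its 4 of 18 missing (22%) lies inside the 19% to 29% range of the traditional limits. This stands: the fault is in which items are counted, not in that share.
- **The endpoint is secondary and the analysis exploratory.** SAP 11.1 has no efficacy power calculation and treats all p-values as exploratory. This bounds the importance but does not make the rule correct.

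**Conclusion.** The rule is wrong as written, because it counts blanks in items other than those it scores. FXS Lethargy can be prorated with up to 7 of 14 items missing, Irritability with 6 or 7 of 18 depending on the reading, Hyperactivity with 3 of 9 and Stereotypic with 2 of 6. These results need only the printed lists and limits.

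The loss of fully answered Hyperactivity or Lethargy subscales rests on the further assumption that *if* means *only if*. It also uses the same-named reading, which the word *corresponding* and the worked example support. On that reading Inappropriate Speech is unaffected because its items are identical in both scorings; Social Avoidance has its own limit.

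All figures are worst cases. A reader might infer that many scores will be distorted or lost, but the documents give no item-level missing rate, so the frequency cannot be estimated. The primary safety analysis is unaffected. The point is worth correcting because it concerns a named secondary endpoint and small arms, and the correction is simple.

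**What to change.** Replace the condition on the traditional subscales with a limit on each FXS subscale's own items, at roughly the share tolerated originally (traditional share × FXS items):

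- Irritability: 0.20 × 18 = 3.6, so 3 or 4 of 18.
- Lethargy: 0.1875 × 14 = 2.6, so 2 or 3 of 14.
- Hyperactivity: 0.1875 × 9 = 1.7, so 1 or 2 of 9.
- Stereotypic: 0.286 × 6 = 1.7, so 1 or 2 of 6.
- Inappropriate Speech and Social Avoidance: 1 of 4 each.

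The sponsor should fix the integers before unblinding. Rounding down throughout would be stricter than the original shares for the first four (17%, 14%, 11% and 17%). Rounding up leaves Stereotypic at its present worst case of 2 of 6.

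State that a fully answered FXS subscale is always scored. Align the worked example with the Irritability limit: at 4 the arithmetic stays and only the justification changes; at 3 the example must be replaced.

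The cost is SAP wording and scoring code. The downside is that a few heavily incomplete forms, now prorated, would become missing.

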8.1.2 Anxiety, Depression, and Mood Scales (ADAMS)

The Anxiety, Depression, and Mood Scales (ADAMS) is a caregiver-completed report that screens comprehensively for anxiety and depression in persons with intellectual disability and consists of 28 items grouped into 5 subscales that assess the frequency and severity of manic/hyperactive behavior, depressed mood, social avoidance, general anxiety, and obsessive/compulsive behavior ([Esbensen et al 2003](#)).

Sub scores will be obtained as follows:

SUBSCALES	Sum of Questions
Manic/Hyperactive behavior	3, 4, 12, 17, 22
Depressed mood	5, 9, 10, 14, 18, 23, 28
Social avoidance	2, 6, 13, 19, 21, 25, 27
General anxiety	1, 3, 7, 11, 15, 24, 26
Obsessive/compulsive behavior	8, 16, 20

Mean change from baseline to Week 2, Week 6, and Week 12 on the ADAMS score and subscale scores will be analyzed as described in [Section 8.1](#). Missing data convention from the provider will be used for missing assessments and scores. Otherwise, missing data from the assessment will be kept as missing.

8.1.3 Repetitive Behavior Scale-Revised (RBS-R)

The Repetitive Behavior Scale-Revised (RBS-R) is a caregiver-completed, 43-item questionnaire assessing a variety of repetitive behaviors with 6 behavior subscales: stereotyped, ritualistic, self-injurious, compulsive, restricted, and sameness ([Bodfish et al 2000](#)).

Overall total RBS-R raw score will be obtained by getting the sum of items 1-43. The number of items endorsed (defined as the number of items rated 1, 2, or 3) and overall will be derived and summarized. Missing data convention from the provider will be used for missing assessments and scores. Otherwise, missing data from the assessment will be kept as missing.

Subscale scores will be computed as follows:

SUBSCALES	Sum of Questions
Stereotyped Behavior	1-6
Self-Injurious Behavior	7-14
Compulsive Behavior	15-22
Ritualistic Behavior	23-28
Sameness Behavior	29-39
Restricted Behavior	40-43

Change from baseline to Week 2, Week 6, and Week 12 on the RBS-R total and subscale raw scores and number of items endorsed will be analyzed as described in [Section 8.1](#).

8.1.4 Conner's 3rd Edition

The Conner's 3rd Edition (Conner's 3; North Tonawanda Multi-Health System, North Tonawanda, NY) is designed to assess attention deficit hyperactivity disorder, and it will be used to collect LAR/caregiver observations of subject behavior. The assessment of behavior in neurodevelopmental disorders, such as FXS, frequently relies upon proxy report. The long form of Conner's 3 is needed to assess inconsistency (reporter reliability) and will be administered at Screening only. The short form of Conner's 3 will be administered as an outcome assessment at the baseline, Week 2, Week 6, Week 12, and EOS visits.

The Inconsistency Index/Response Style Analysis is a categorical variable obtained using two variables obtained at the Screening visit using the long form of Conner's 3: Inconsistency Index Raw Score and Inconsistency Index Number of Differentials ≥ 2 . If the Inconsistency Index Raw Score ≥ 7 and Inconsistency Index Number of Differentials ≥ 2 , then there is a possible inconsistent response style. These data will be summarized and listed.

The Raw sub scores for Content scales will be provided in the eCRF. Content scales include inattention, hyperactivity/impulsivity, learning problems, executive functioning, defiance/aggression, peer relations. The mean change of content subscale scores at Week 2,

Week 6, and Week 12 from baseline will be analyzed as described in [Section 8.1](#). Subjects with inconsistent response style at Screening visit were excluded. Missing data convention from the provider will be used for missing assessments and scores. Otherwise, missing data from the assessment will be kept as missing.

8.1.5 Short Sensory Profile-2

The Short Sensory Profile-2 is a caregiver questionnaire to evaluate a subject's sensory processing patterns in the context of home, school, and community-based activities.

Sensory Processing Raw Total score is the sum of items 1-14 and Behavioral Responses Raw Total score is the sum of items 15-34. Raw scores of the subscales will be derived as follows and will be analyzed as described in [Section 8.1](#):

SUBSCALES	Sum of Questions
Seeking	6-8, 11, 14, 31, 32
Avoiding	16-20, 22-24, 26
Sensitivity	1-5, 21, 25, 28, 29, 33
Registration	9, 10, 12, 13, 15, 27, 30, 34

Change from baseline in Sensory Processing Raw Total score, Behavioral Responses Raw Total score and subscale scores at Week 2, Week 6, and Week 12 will be analyzed as described in [Section 8.1](#). Missing data convention from the provider will be used for missing assessments and scores. Otherwise, missing data from the assessment will be kept as missing.

8.1.6 Clinical Global Impressions Scales

The CGI-S scale will be used by the investigator to assess the severity of symptoms, and the CGI-I scale will be used by investigators to assess improvement from baseline. The CGI-S has been adapted to capture specific characteristics commonly present in the FXS population. Both CGI-S and CGI-I will be conducted by a clinician with experience in FXS.

A dichotomous responder variable will be defined whether or not there is improvement in any CGI-I. Response is defined as improvement in any of the CGI-I survey questions, with improvement indicated by a response of "Very much improved", "Much improved", and "Minimally improved" compared to time of enrollment. The CGI-I responder endpoint will be compared between treatments (OV101 5mg vs. OV101 10mg; OV101 5mg vs. OV101 15mg; OV101 10mg vs. OV101 15mg) at week 12 and exact test will be used to test for the difference of the treatments.

CGI severity (CGI-S) and CGI improvement (CGI-I) scores as well as by-domain CGI-S sub scores will be provided in the eCRF Domains includes: Anxiety, ADHD, Communication/Connectedness, Repetitive and Restrictive Behavior, Disruptive Behavior, and Activities of Daily Living.

The mean change of CGI-S score and by-domain CGI-S sub scores at Week 2, Week 6, and Week 12 from baseline will be analyzed as described in [Section 8.1](#).

The frequencies of CGI-I categories at Week 2, Week 6, and Week 12 will be summarized.

Responder analysis will be performed to test difference in CGI-I between treatments with exact test at Week 12 using observed data. Additionally, a sensitivity analysis will be conducted at Week 12 using last observation carried forward (LOCF) method for missing data.

8.2. Exploratory Efficacy Analysis

8.2.1 Caregiver-Completed Endpoints

8.2.1.1 Behavior Assessment System for Children, 3rd Edition (BASC-3 PRQ)

The Behavior Assessment System for Children, 3rd Edition, Parenting Relationship Questionnaire (BASC-3 PRQ) provides information on the relationship between a caregiver and a child across multiple dimensions ([Pearson, New York, NY](#)). It yields the following subscale scores: attachment, communication, discipline practices, involvement, parent confidence, satisfaction with school, and relation frustration. The questionnaire is written at a third grade level and also calculates a number of response validity scores, such as consistency and response pattern, to detect careless or exaggerated responding. It includes normative samples for both female and male raters that are closely matched to the US Census population estimates.

Content Domains raw scores (Attachment, Communication, Discipline, Involvement, Parenting Confidence, Satisfaction with School, and Relationship Frustration) at Week 6 and Week 12 will be summarized. Missing data convention from the provider will be used for missing assessments and scores. Otherwise, missing data from the assessment will be kept as missing.

Validity Index Summary Raw Scores and Category Assignment (F Index, D Index, Response Pattern Index, and Consistency Index) will be summarized.

8.2.1.2 Parent Global Impressions Scales

The Parent Global Impressions-Severity (PGI-S) scale will be completed by the LAR/caregiver to assess the severity of symptoms, and the Parent Global Impressions-Improvement (PGI-I) scale will be used by the LAR/caregiver to assess improvement from baseline. The PGI-S has been adapted to capture specific characteristics commonly present in the FXS population.

Severity of Participant's condition will be collected in the eCRF and the change from baseline at Week 2, Week 6, and Week 12 will be analyzed as described in [Section 8.1](#).

Improvement of Participant's condition will be collected in the eCRF and the frequencies at Week 2, Week 6, and Week 12 will be summarized. Missing data convention from the provider will be used for missing assessments and scores. Otherwise, missing data from the assessment will be kept as missing.

8.2.1.3 Pediatric Quality of Life Inventory

The Pediatric Quality of Life Inventory (PedsQL) generic core scales and Multidimensional Fatigue Scale will be administered in this study ([Varni et al 2004](#)). The generic core scales include 23 items covering the domains of physical, emotional, social, and school functioning. The Multidimensional Fatigue Scale contains 18 items measuring general fatigue, sleep/rest fatigue, and cognitive fatigue.

PedsQL Generic Core and Multidimensional Fatigue transformed scores, mean scores for the domains, and total scores will be derived. Each item will be reverse scored and linearly transformed to a 0-100 scale, so that higher scores indicate better Health-Related Quality of Life. Items will be transformed as follows: 0=100, 1=75, 2=50, 3=25, and 4=0.

Transformed scores will be used to calculate the 3 mean domain scores, and total score on the multidimensional fatigue scale as follows:

DOMAIN	Mean Score*
General Fatigue	Mean of 6 transformed items under 'General Fatigue'
Sleep/Rest Fatigue	Mean of 6 transformed items under 'Sleep/rest Fatigue'
Cognitive Fatigue	Mean of 6 transformed items under 'Cognitive Fatigue'
Total	Mean of all transformed items

* If more than 50% of the items in the scale are missing, the mean domain score should not be computed. If more than 50% of the items are completed, mean of the completed items in a domain scale will be imputed.

Transformed scores will be used to calculate the 4 mean domain scores, total score, and Psychosocial Health Summary Score on the generic core scale as follows:

DOMAIN	Mean Score*
Physical Functioning	Mean of 8 transformed items under 'Physical Functioning'
Emotional Functioning	Mean of 5 transformed items under 'Emotional Functioning'
Social Functioning	Mean of 5 transformed items under 'Social Functioning'
School Functioning (for Teens ages, 13-18) or Work/Studies Functioning (for Young Adults, ages 18-22)	Mean of 5 transformed items under 'School Functioning" or 'Work/Studies Functioning'

Psychosocial Health Summary Score	Mean of transformed items under 'Emotional Functioning', 'Social Functioning', and "School Functioning" or 'Work/Studies Functioning' mean scores
Total	Mean of all transformed items

* If more than 50% of the items in the scale are missing, the mean domain score should not be computed. If more than 50% of the items are completed, mean of the completed items in a domain scale will be imputed.

Change from baseline in the mean total score and mean scores of the domains for both PedsQL generic core and multidimensional will be analyzed at week 6 and EOT.

8.2.1.4 Children's Sleep Habits Questionnaire

The Children's Sleep Habits Questionnaire (CSHQ) is a caregiver-completed assessment of sleep behaviors in children and adolescents ([Owens et al 2000](#)). The abbreviated version of this questionnaire includes 33 items that assess sleep habits and possible difficulties with sleep. The LAR/caregiver will be asked to recall the subject's sleep behaviors over the preceding week.

The CHSQ consists of 8 domains with their sub scores and will be derived as follows:

Domains	Derivation
Bedtime Resistance	sum of items 1R, 3R, 4, 5, 6, and 8
Sleep Onset Delay	item 2R
Sleep Duration	sum of items 9, 10R, and 11R
Sleep Anxiety	sum of items 5, 7, 8, and 21
Night Wakings	sum of items 16, 24, and 25
Parasomnias	sum of items 12, 13, 14, 15, 17, 22, and 23
Sleep Disordered Breathing	sum of item 18, 19, and 20
Daytime Sleepiness	sum of items 26R, 27, 28, 29, 30, 31, 32, and 33

R- reversed scored.

Analysis as described in [Section 8.1](#) will be used to analyze the change from baseline in CHSQ domains at Week 2, Week 6, and Week 12.

Subscale scores of CSHQ are not calculated if $\geq 50\%$ of the subscale answers are missing. When $< 50\%$ of subscale answers are missing, the subscale score will be prorated following the steps described in [Section 8.1.1](#). For example, 4 out of 6 Bedtime Resistance questions are answered with a sum of 9, then the prorated score of Bedtime Resistance is $(6/4)*9=13.5$.

CSHQ total will be calculated if all subscales are not missing.

